7.2. Method of recruitment

Subjects will be recruited at the COVID-19 hospitalization ward at the participating centers. The study will be proposed by the treating physician to all subjects with PCR-Confirmed COVID-19 infection and a presence of acute hypoxic respiratory failure.

There will be no compensation for study participation. Partner Therapeutics Inc. is providing sargramostim to the study subjects, free of charge.

Since this is a hospital based trial, taking place over a minimum of five days in which patients are severely ill, we suspect the retention in the trial to be high.

7.3. Screening

Patients will be informed about the study by the treating physician.

After receiving full explanation, having received sufficient time to consider the trial, asking questions and receiving satisfying responses to all questions, patients will be asked to sign ICF.

A serum pregnancy test will be done (female patients only).

Medical history will be checked for review of exclusion criteria and relevant subject information.

Patients will be continuously monitored on the COVID-19 ward.

Exams (standard of care) include, but are not limited to:

- ECG
- Chest X-Ray, and CT-scan
- Laboratory tests for leukocyte formula, kidney and liver function, ferritin levels
- Vital signs
- Pulse oximetry, Arterial blood gas, capnography

As soon as all in- and exclusion criteria are checked and patient is considered eligible, patient can be randomized. There is no minimal window to randomize the patient.

8. Investigational Medicinal Product (IMP)

8.1. Name of the IMP

LEUKINE®

8.1.1. Composition and active substance of the IMP

Sargramostim, Granulocyte macrophage colony-stimulating factor (GM-CSF), is the active substance of Leukine®.

8.1.2. Producer and Distributor of the IMP

The producer and distributor of Leukine® is Partner Therapeutics Inc, an integrated commercial-stage biotech company focused on the development and commercialization of therapeutics that improve health outcomes in the treatment of cancer. The distribution of IMP will be done by Tanner Pharma.

8.1.3. Preparation + Dosage + administration of the IMP

For inhalation: LEUKINE® is a sterile, preservative-free lyophilized powder that requires reconstitution with 4mL normal saline solution, to reach a concentration of 62,5 mcg/ml. Once reconstituted, LEUKINE® can be inhaled as an aqueous aerosol using either a vibrating mesh nebulizer or jet nebulizer, aerosolizing 2 ml twice daily. Reconstituted LEUKINE® solution for inhalation should be used within 16 hours following reconstitution and/or dilution. Dosage for inhalation: 125mcg twice daily via nebulizer. Nebulizing is preferably done in an isolation negative pressure chamber, and if not, personnel should use an FFP2 mask. Patient should self-administer the medication and where possible, the room should not be entered within one hour after administration.

For intravenous injection: LEUKINE® injection in 0.9% Sodium Chloride Injection, USP. Dilute LEUKINE® for intravenous infusion in 0.9% Sodium Chloride Injection, USP. If the final concentration of LEUKINE®

is below 10 mcg/mL, add Albumin (Human) at a final concentration of 0.1% to the saline prior to addition of LEUKINE to prevent adsorption to the components of the drug delivery system. To obtain a final concentration of 0.1% Albumin (Human), add 1 mg Albumin (Human) per 1 mL 0.9% Sodium Chloride Injection, USP (e.g., use 1 mL 5% Albumin [Human] in 50 mL 0.9% Sodium Chloride Injection, USP). Once diluted for infusion, LEUKINE® is stable for 6h. Dosage for intravenous injection: 125mcg/m²/day over a 4-hour period for up to 5 days.

8.1.4. Permitted dose adjustments and interruption of treatment

No dose adjustments and interruptions are permitted during this trial. In case of anaphylaxis or severe AE, the drug will be immediately interrupted.

8.1.5. Duration of treatment

LEUKINE® will be administered for 5 days, with a possible 5 day extension to a maximum of 10 days in case of progression of disease and need for mechanical ventilation.

8.1.6. Packaging and Labeling of the IMP

LEUKINE® (sargramostim) for injection is a sterile, preservative-free, white lyophilized powder supplied in a carton containing five 250 mcg single-dose vials.

LEUKINE® (sargramostim) injection is a sterile, clear, colorless solution preserved with 1.1% benzyl alcohol supplied in a carton containing one 500 mcg/mL multiple-dose vial and a carton containing five 500 mcg/mL multiple-dose vials (NDC 0024-5844-05).

Storage and Handling : Leukine should be stored at 4 °C.

Drug will be labeled by Pharmacy UZ Ghent (for UZ Ghent enrolment) for inhaled or intravenous use.

8.1.7. Storage conditions of the IMP

Store LEUKINE® vials refrigerated at 2°C-8°C (36°F-46°F) in the original carton to protect from light. Do not freeze or shake. Do not use beyond the expiration date printed on the vial.

Leukine® is to be shipped refrigerated at 2°C-8°C (36°F-46°F). The medication will be delivered to the pharmacy of the participating centers. Temperature during shipment and storage is to be monitored continuously. Whenever a temperature deviation occurs, Partner Therapeutics Inc. should be contacted. Partner Therapeutics Inc. might allow further use of the medication vials depending on the duration and intensity of the temperature excursion. The co-ordinating investigator should be informed of this deviation as well.

8.1.8. Known side effects of the medication

To date, there have been no new safety signals associated with LEUKINE® (sargramostim). Observed side effects with aerosolized LEUKINE® at 250mcg dose and in at least one evaluation have included: bronchospasm, cough, dyspnea, a decrease in vital capacity and/or forced expiratory volume associated with bilateral infiltrates, pleural effusions, increased phlegm, throat irritation, and back pain.

8.2. Concomitant / Rescue Medication

There are no restrictions regarding concomitant/rescue medication.

9. Study Specific Procedures

Patients will be informed about the study by the treating physician.

After receiving full explanation, having received sufficient time to consider the trial, asking questions and receiving satisfying responses to all questions, patients will be asked to sign ICF.

The ICF process will be performed before any other study related procedure.

9.1. Randomization

In this open label trial patients will be randomized in a 1:1 ratio. Randomization in Belgium will be done using REDCap (electronic IVRS system).

9.2. Study specific interventions

This is a hospital based intervention trial, in which patients with COVID-19 will be treated at least for 5 days with sargramostim. Patients with COVID-19 infection and respiratory failure are severely ill, and will require multiple daily clinical exams, blood sampling, vital parameter measurements, blood oxygenation measurements, and chest X-rays. These are all part of the clinical management plan of the patients, and data stored in the electronic patient file will be used as part of the assessment of efficacy and safety profile of sargramostim.

On screening, blood sample will be taken, preferentially during routine blood sampling, to determine exclusion criteria (pregnancy, high ferritin level).

On day 1, prior to sargramostim treatment in group A, and during the day in group B control patients, a tube of blood serum (5 ml) and an EDTA tube (10 ml) will be collected for measuring blood cytokine and chemokine levels, and activation of immune cells in selected centers. Also in each center, an arterial blood gas determination via arterial puncture will be taken. This sample should be taken in an upright position, while breathing room air for a minimum of 3 minutes. If this is impossible due to dependency on supplemental oxygen, FiO₂, oxygen flow rate, and method of oxygen delivery should be noted in the patient file. If arterial blood gas is taken within 24h before first dose administration, the arterial blood gas of screening can be used as D1 value.

Method	O ₂ flow (l/min)	Estimated FIO ₂ (%)
Nasal	≤ 1,5	24
	> 1,5 and ≤ 2,5	28
	> 2,5 and ≤ 3,5	32
	> 3,5 and ≤ 4,5	36
	> 4,5 and ≤ 5,5	40
	> 5,5 and ≤ 15	44
Nasal pharyngeal cannula	≤ 0,5	24
	> 0,5 and ≤ 1	28
	> 1 and ≤ 1,5	30
	> 1,5 and ≤ 2,5	32
	> 2,5 and ≤ 3,5	36
	> 3,5 and ≤ 4,5	40
	> 4,5 and ≤ 5,5	50
Face mask	> 5,5 and ≤ 6	60
	≤ 1,5	24
	> 1,5 and ≤ 2	28
	> 2 and ≤ 2,5	30
	> 2,5 and ≤ 3,5	32
	> 3,5 and ≤ 4	36
	> 4 and ≤ 4,5	38
	> 4,5 and ≤ 5,5	40
Face mask with reservoir	> 5,5 and ≤ 7	50
	> 7	60
	≤ 2,5	28
	> 2,5 and ≤ 3,5	32
	> 3,5 and ≤ 4,5	40
	> 4,5 and ≤ 5,5	50
	> 5,5 and ≤ 6,5	60
	> 6,5 and ≤ 7,5	70
	> 7,5 and ≤ 8,5	80
	> 8,5 and ≤ 9,5	90
	> 9,5	95

On day 6 or on day of discharge before day 6 , a tube of blood serum (5ml) and an EDTA tube (10 ml) will be collected for measuring blood cytokine and chemokine levels, and activation of immune cells in selected centers. Also in each center, an arterial blood gas determination via arterial puncture will be taken.

On days 1-5, patients in group A will inhale sargramostim 125mcg twice daily for 5 days as a nebulized inhalation using a Philips InnoSpire Go portable mesh nebulizer on top of standard of care. This device is a handheld mesh nebulizer that can be fitted with a facial mask. Patients will be instructed prior to receiving the first dose on how to use this simple device, by a physician. This procedure is finished in 5-10 minutes, and will be performed twice daily, in the morning (between 6 a.m. and 11 a.m.) and evening (between 6 p.m. and 11 p.m.).

Upon progression of disease requiring initiation of non-invasive or invasive mechanical ventilatory support within the 5 day period, in patients in the active group, inhaled sargramostim will be replaced by intravenous sargramostim 125mcg/m² body surface area once daily until the 5 day period is reached. This administration will occur via a centrally placed catheter or peripheral catheter, that will be in place as part of routine medical care at the ICU.

On a final clinical visit between week 10-20 an additional serum tube (5ml) and an EDTA tube (10 ml) will be taken in selected centers.

9.3. Overview of collected data

1. patient demographics
 - age, sex, ethnicity, day of admission
2. day of COVID-19 PCR positivity, and conversion to negative
2. patient biometry
 - weight, length, BMI, body surface area
3. Clinical and laboratory parameters on screening day and during trial
 - first day of illness, potential source of infection
 - clinical examination findings (cyanosis, crepitation's and rales, heart murmurs, peripheral edema)
 - vital signs (temperature, blood pressure, heart rate, breathing rate)
 - pulse oximetry data (SaO₂)
 - clinical blood gas sampling (PaO₂, PaCO₂, HCO₃)
 - clinical chemistry sampling (ferritin, leukocyte formula, platelets, kidney and liver function, fibrinogen, triglycerides)
 - Chest X-ray and/or CT characteristics and radiology clinical report
 - in case of admission to ICU : invasive monitoring data (arterial blood pressure, PCWP, continuous O₂ saturation, continuous ECG, ventilatory parameters (tidal volume, FiO₂, PEEP pressure, peak pressure, minute ventilation)
4. All standard care drugs used during the trial and on day of enrolment of the trial, including oxygen flow rate.
5. Basic clinical data on prior medical history (prior lung diseases, smoking history, prior lung function measurements (preferentially within 5 preceding years), prior gas exchange measurements) and medication use will be collected from electronic medical record.
6. Study specific measurements

On serum samples from selected centers, at each of the indicated timepoints exploratory analysis may include but is not limited to:

- Anti-drug antibodies (ADA) (D1-D6-FU) using ELISA
- Quantification of sRAGE (D1-D6-FU) using ELISA
- Quantification of Ang2 (D1-D6-FU) using ELISA
- Quantification of MUC1 (D1-D6- FU) using ELISA
- Quantification of GDF15 (D1-D6- FU) using ELISA
- Quantification of suPAR (D1-D6-FU) using ELISA
- Quantification of cytokines GM-CSF, IL-1b, IL1RA, IL-6, IL-8, IL-10, IL12p40, IL17A, IL-18, IL23p19, CCL2, CXCL9, CXCL10, INFgamma, TNF (D1-D6-FU) using Luminex at VIB-UGhent.
- Quantification of IFNalpha2 (D1-D6-FU) using SIMOA
- Quantification of GM-CSF (D1-D6-FU) using MSD.
- Quantification of S1 specific IgG and IgA antibodies (D1-D6-FU) using ELISA
- Quantification of NCP specific IgG (D1-D6-FU) using ELISA
- will be measured on samples collected at the various centers at day 1 or day 6 or discharge (whichever comes first) and at 12-22 weeks follow up visit.

Peripheral blood mononuclear cells will be prepared at UZ Gent, following shipment of EDTA-blood samples by selected centers, for Immunomonitoring purposes on D1, and D6 (or at hospital discharge, if earlier) and follow up visit. PBMC samples will be vitally frozen until analysis. When all samples are available from the selected centers, they will be thawed and PBMCs will be analyzed by the Primary Immunodeficiency Lab at UZ Ghent, in collaboration with the VIB-UGent Center for Inflammation Research. VIB-UGhent will perform some these assays as a service to UZGhent labs. Analyses will include :

- flow cytometry analysis of numbers of peripheral blood lymphocyte and monocyte subsets, and their activation status by flow cytometry
- ELISPOT assays to measure the number of IFNg, TNFa, IL-2 and GM-CSF producing CD4 and CD8 T cells following restimulation of frozen and thawed peripheral blood mononuclear cells (PBMC) with a SARS-CoV2 megapool of immunogenic peptides.

9.4. Schematic overview of the data collection & interventions

10. Procedure	Screening	D1	D2-D5	D6/discharge	D7-D9	D10	Follow-up (10-20 weeks after D1)
Informed consent	X						
Inclusion/exclusion criteria	X						
Randomization		X					
Medical history & biometry	X						
Anamnesis and (S)AE inquiry	X						X
Concomitant medication	X						X
Physical examination ^l	X						X
6 Minutes Walk Test ^{o, i}							X
Vital signs ^a	X						X
ECG ^l				On clinical grounds			
Chest X-ray and/or (HR)CT scan				On clinical grounds			X ^m
Lung function ^l							X
Routine laboratory assessments^l on clinical grounds, except:	X	X ^b		X ^c			X ^c
- screening/day 1 and day 6/discharge							
Serum pregnancy test	X						
Study blood sampling							
- 5 ml serum tube		X		X			X
- 10 ml EDTA tube (selected centers only)							
Arterial blood gas^d		X		X			X
Score assessments							
- 6-point ordinal scale ^e							X
- Clinical sign score ^f							X
- NEWS2 score ^g							X
- SOFA score ^h		X		X		X	X
- HScore ⁱ		X		X			X
- CURB-65 ^j		X					

SARPAC

- APACHE II ^k		X					
- Glasgow Coma Scale	→						X
- HRCT fibrosis score ^m							X
IMP ⁿ		(X)	(X)	(X)	(X)	(X)	
Drug compliance		→					

^a Includes morning assessment (7-10 am) of T°C (actual and highest last 24h), Pulse rate, Blood Pressure, Respiratory Rate, SpO2 by pulseoximetry. Time point assessment (7-10 am) is not applicable for the Follow-Up visit.

^b Should minimally include haemoglobin, platelets, WBC count, eosinophils, lymphocytes, CD4 and CD8 T cell count, CRP, bilirubin, AST, ALT, LDH, creatinine, fibrinogen, triglycerides, ferritin, ureum, troponin, D-dimers.

^c Should minimally include haemoglobin, hematocrit, platelets, WBC count, neutrophils, eosinophils, lymphocytes, CD4 and CD8 T cell count, CRP, bilirubin, AST, ALT, LDH, creatinine, fibrinogen, triglyceride, ferritin, troponin, D-dimers, ESR, CK

^d Patient sitting upright breathing room air for a minimum of 3 minutes. If this is impossible due to dependency to supplemental oxygen, FiO2, oxygen flow rate, and method of oxygen delivery should be noted in the patient file. If arterial blood gas is taken within 24h before first dose administration, the arterial blood gas of screening can be used as D1 value.

^e Defined as 1 = Death; 2 = Hospitalized, on invasive mechanical ventilation or ECMO; 3 = Hospitalized, on non-invasive ventilation or high flow oxygen devices; 4 = Hospitalized, requiring supplemental oxygen; 5 = Hospitalized, not requiring supplemental oxygen; 6 = Not hospitalized.

^f (0-18) by scoring 6 clinical signs from 0 to 3 (0 = absent, 1 = mild, 2 = moderate and 3 = severe): Fever (0 = <37°C; 1 = 37.1-38°C; 2 = 38.1-39°C; 3 = >39°C) last 24h; Cough; Fatigue; Shortness of breath; Diarrhea; Body pain.

^g NEWS2 (see <https://www.mdcalc.com/national-early-warning-score-news-2>): requires RR, SpO2, T°C, SBP and pulse.

^h SOFA score (see <https://www.mdcalc.com/sequential-organ-failure-assessment-sofa-score>): requires PaO2, FiO2, platelet count, GCS, bilirubin, MAP and creatinine.

ⁱ HScore (see <https://www.mdcalc.com/hscore-reactive-hemophagocytic-syndrome>): requires T°C, haemoglobin, WBC count, platelets, ferritin, triglycerides and AST (BM aspirate is not required).

^j CURB-65 (see <https://www.mdcalc.com/curb-65-score-pneumonia-severity>): requires confusion, BUN, RR, blood pressure and age.

^k APACHE II (see <https://www.mdcalc.com/apache-ii-score>): requires age, T°C, MAP, pH, pulse, RR, sodium, potassium, hematocrit, creatinine, WBC count, GCS and FiO2.

^l Intervention is standard of care and is being performed regardless of inclusion in the study.

^m Preferably HRCT if done per standard of care, which will be used to evaluate fibrosis at follow visit. This is a subjective assessment of the overall extent of normal attenuation, reticular abnormalities, honeycombing and traction bronchiectasis will be performed. A reticular abnormality is defined as a collection of innumerable areas of small linear opacity. Honeycombing is defined as the presence of a cystic airspace measuring 3-10 mm in diameter, with 1- to 3-mm thick walls. Traction bronchiectasis is defined as irregular bronchial dilatation within the surrounding areas showing parenchymal abnormalities. The morphological criteria on HRCT scans include bronchial dilatation with respect to the accompanying pulmonary artery, a lack of tapering of the bronchi and the identification of bronchi within 10 mm of the pleural surface. The HRCT findings will be graded on a scale of 1-4 based on the classification system: 1. normal attenuation; 2. reticular abnormality; 3. traction bronchiectasis; and 4. honeycombing. The presence of each of the above four HRCT findings will be assessed independently in three (upper, middle and lower) zones of each lung. The upper lung zone is defined as the area of the lung above the level of the tracheal carina, the lower lung zone is defined as the area

SARPAC

of the lung below the level of the inferior pulmonary vein and the middle lung zone is defined as the area of the lung between the upper and lower zones. The extent of each HRCT finding will be determined by visually estimating the percentage (to the nearest 5%) of parenchymal involvement in each zone. The score for each zone will be calculated by multiplying the percentage of the area by the grading scale score. The six zone scores will be averaged to determine the total score for each patient. The highest score is 400 points and the lowest score is 100 points using this calculation method. The total score is the “HRCT fibrosis score”. (<https://www.ncbi.nlm.nih.gov/pmc/articles/PMC3922654/pdf/1465-9921-15-10.pdf>)

^a Patients randomized in the treatment group will receive inhaled sargramostim from D1 until D5. In case of progression requiring mechanical ventilation within the first 5 days, IV sargramostim can be initiated until the 5 day period is reached. From day 6 onwards, progressive patients in the active group will have the option to receive an additional 5 days of IV sargramostim, based on the treating physician’s assessment. Patients in the control group will have the option to receive 5 days of IV sargramostim in case of progression requiring mechanical ventilation, based on the treating physician’s assessment. IMP should always be administered after other assessments, where possible.

^o 6 MWT: to assess the distance walked over 6 minutes as submaximal test of aerobic capacity/endurance.

10.1. Restrictions for subjects during the study

There are no subject restrictions during this trial.

11. Sampling

11.1. Types and number of samples

D1: serum blood sample 5ml, EDTA blood sample 10 ml

D6 or discharge before day 6 : serum blood sample 5ml, EDTA blood sample, 10 ml

W10-20 follow-up visit : serum blood sample 5ml, EDTA blood sample, 10 ml

EDTA blood samples should only be collected in selected sites.

11.2. Timepoints of sampling

These samples are to be taken on D1 and D6 (or discharge if before day 6) and on final follow up visit between week 10 and 20. There's no time window allowed.

11.3. Sample Handling & Analysis

In all centers samples will be taken during hospitalization together with the blood draw for standard of care.

After clotting for 30-60 minutes the samples will be processed at 1770 g during 10 minutes at room temperature. 3 aliquots will be filled and frozen at -80°C until further analysis.

Centrifugation and storage will be done by qualified personal.

EDTA blood samples (only for selected sites) will be processed to purify peripheral blood mononuclear cells (PBMC) by gradient centrifugation and stained for flow cytometric analysis of number of monocytes, HLA-DR expression on monocytes and dendritic cells, and lymphocyte activation, described under 4.3. Flow cytometry will be performed on paraformaldehyde fixed samples.

Multiple cytokines and chemokines will be measured by multiplex bead based ELISA assay, described under 4.3. Development of anti-drug antibodies (ADA) will be measured using protocol developed by PartnerTherapeutics on serum samples taken at day 1 and follow up visit.

11.4. Sample Storage and/or shipping

Serum samples will be stored at minus 20 degrees temperature at the participating research centers. These samples will be shipped to sponsor at regular intervals, and in any case at the end of the study. In selected samples, EDTA blood will be collected for flow cytometry analysis and shipped to the PID lab at UZGhent for purification of PBMCs, freezing and later flow cytometry. These samples will be shipped same day (with a 24h tolerance) to UZGhent.

Frozen PBMC's may also be analyzed in specific participating centers if this was agreed with PI of the study. Storage conditions of frozen PBMCs is at -80°C prior to thawing and flow cytometry analysis.

For all sites where PBMC manipulation is being done at site for analysis at that site, samples will be destroyed at the end of the study. For samples which go directly to PID lab at UZGhent, for purification of PBMCs, freezing and later analysis. VIB shall help in the analysis of flow cytometry experiments, but

will not become the owner of the samples, nor of the data ensuing from those samples. At all times, UZGhent remains the owner of the samples and data resulting from these analyzes by VIB.

11.5. Future use of stored samples

Initially samples will be stored for the use as described within this protocol. If at a later time point samples will be stored for future use, they will be stored in a FAGG certified biobank. In that scenario, the Ethics comite of UZGhent will be asked for permission to store the material in a FAGG certified biobank. If permission is not granted, samples will be destroyed after completion of the study.

12. Statistical Considerations

12.1. Sample size calculation

The outcome(s) on which the sample size calculation is based upon, is the primary endpoint measurement of oxygenation, defined as ratio of $\text{PaO}_2/\text{FiO}_2$ and P(A-a)O_2 .

Sample calculation and power analysis have been performed using Genstat. The target difference is the difference measured at the primary endpoint (at day 6) between the control and the treated group. Given a sample size of 40 patients each, a minimal improvement of 10% in the treated group relative to the control group will be detected as significant at a significance level of 0,01 with a power of 0.90. The error variance was set at 100 units, corresponding with a standard deviation of 10 units.

The post-treatment evaluations should be assessed within 24 hours of the last dose of treatment. That is, Day 6 will be the timepoint for measures of efficacy endpoints based on 5 days of treatment, and Day 10 for patients who complete 10 days of treatment. If the patient is discharged from hospital prior to the day 6 (or day 10) efficacy evaluations, the values at day of discharge will be used as value for measuring efficacy endpoints.

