4.1. Primary End Points + Time Points

To measure the effectiveness of sargramostim on restoring lung homeostasis, the **primary endpoint** of this intervention is **measuring oxygenation** after 5 DAYS of inhaled (and intravenous) treatment through assessment of pretreatment (day 0) and post-treatment (day 5) ratio of PaO₂/FiO₂ and through measurement of the P(A-a)O₂ gradient, which can easily be performed in the setting of clinical observation of patients admitted to the COVID -19 ward or ICU COVID-19 unit. Preferentially, this measurement should be done in the upright position, while breathing room air for a minimum of 3 minutes. If this is impossible due to need for supplemental oxygen, FiO₂ and oxygen supplementation method should be recorded in patient record, so that A-a gradient can be normalized for age expected normal A-a gradient while on supplemental oxygen use.

During the 5 day treatment period, we will perform daily measurements of oxygen saturation (pulse oximetry) in relation to FiO₂, and the slope of alterations in this parameters could also be an indicator that our hypothesis is correct.

If the patient leaves hospital prior to the day 6 analysis point, oxygenation at day of discharge will be used as value for measuring primary endpoint.

Improvement will be expressed as % of patients showing an improvement in $P(A-a)O_2$ gradient and PaO_2/FiO_2 ratio between day 6 and day 1 of at least 25%; at least 33% and at least 50% in each treatment arm and expressed also as mean and median change in $P(A-a)O_2$ gradient and PaO_2/FiO_2 ratio comparing D6 to D1 in both treatment arms.

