12.2. Type of statistical methods

All endpoints will be summarized and where relevant represented graphically

A detailed statistical analysis plan (SAP) has been set up by EffectStats LLC, Cambridge Massachusetts, USA. The statistical tests to be used to look at improvements in oxygenation between treatment groups will be a Chi-square test. Mortality frequencies will be analyzed using Wald test.

Key timepoints of interest for endpoints include Day 6 and Day 11, where data are available. All available efficacy data will be tabulated and presented for all patients in the mITT Population.

Oxygenation after 5 days of Sargramostim Intervention

To measure the effectiveness of sargramostim on restoring lung homeostasis, the primary endpoint of this intervention is measuring oxygenation after 5 days of inhaled (and intravenous) treatment through assessment of pretreatment and post-treatment ratio of $\text{PaO}_2/\text{FiO}_2$, $\text{SpO}_2/\text{FiO}_2$ and through measurement of the P(A-a)O_2 gradient. During the 5 day treatment period, daily measurements of oxygen saturation (pulse oximetry) in relation to FiO_2 will be performed. Negative value of P(A-a)O_2 gradient would be removed from the primary analysis.

P(A-a)O_2 gradient, $\text{PaO}_2/\text{FiO}_2$ ratio and $\text{SpO}_2/\text{FiO}_2$ are defined as:

$\text{P(A-a)O}_2 \text{ gradient} = [(\text{FiO}_2) \times (\text{Atmospheric Pressure} - \text{H}_2\text{O Pressure}) - (\text{PaCO}_2/0.8)] - \text{PaO}_2$

$\text{PaO}_2/\text{FiO}_2 = \text{Partial Pressure Oxygen/Fraction of Inspired Oxygen} \times 100$

$\text{SpO}_2/\text{FiO}_2 = \text{Oxygen Saturation/ Fraction of Inspired Oxygen} \times 100$

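### The 0.90 power in section 12.1 can belong only to a comparison of means, so it does not cover the chi-square test that section 12.2 names for oxygenation improvement

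*Protocol*

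**What the plan says.** Protocol section 12.1 sets the sample size. It plans 40 patients per arm and promises that "a minimal improvement of 10% in the treated group relative to the control group will be detected as significant at a significance level of 0,01"; the stated power is 0.90. The variability input is: "The error variance was set at 100 units, corresponding with a standard deviation of 10 units". The target is the difference between arms at Day 6. No responder rate, control mean, sidedness or test is given.

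Section 12.2 names two tests for that comparison.
- Near its start: "The statistical tests to be used to look at improvements in oxygenation between treatment groups will be a Chi-square test".
- Further on, for group A against group B, it says that the difference in change from baseline is compared by a t-test, and it makes Day 6 the primary analysis point.

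Section 4.1 gives the primary endpoint first in responder form: "Improvement will be expressed as % of patients showing an improvement in" the gradient and the PaO2/FiO2 ratio of at least 25%, 33% or 50%. Mean and median changes come second. Section 12.2 repeats the three cut-offs for the gradient as results to be summarised.

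**The concern.** A variance, an SD and a between-arm difference are the inputs of a two-sample comparison of means. The power of a chi-square test on responder percentages depends instead on the two responder rates, and the protocol gives none. Splitting a continuous outcome at a cut-off also discards the size of each patient's change, so on the same data the split test has less power.

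A reader who meets one power figure in 12.1 and a chi-square test at the start of 12.2 may well join the two. A non-significant responder result would then be taken as evidence against an effect that the trial was said to be 90% sure to detect, although that assurance was never calculated for the responder test.

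**Working it through.** **Inputs.** n = 40 per arm and alpha 0.01 (section 12.1); 1:1 allocation (section 9.1); SD 10 units (section 12.1). Assumptions: two-sided testing, normal outcome, equal SD in both arms, no missing data. The standardised difference d is not given, so two readings are shown.

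**1. The plan's own figure, as a comparison of means.** Normal approximation: power = Φ(d·√(n/2) − 2.576), with √(40/2) = 4.472.
- Reading 10% as 10 units gives d = 1.0: Φ(4.472 − 2.576) = Φ(1.896) = 0.971. The noncentral t gives 0.964. The printed 0.90 is not reproduced; on this reading it is conservative.
- Working back from 0.90: difference = (2.576 + 1.282) × 10 × √(2/40) = 8.63 units. The t version gives 8.81 units, or 0.88 SD. This difference is derived here and is not a planning input of the protocol. As a multiple of the SD, it holds whatever the units.

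**2. Chi-square on the same outcome, split at a cut-off.** With responder rates p1 (control) and p2 (treated), Φ⁻¹(p2) = Φ⁻¹(p1) + d. The most favourable cut-off lies midway between the two means, so p1 = Φ(−d/2) and p2 = Φ(d/2). The approximate power is

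Φ{ [ (p2 − p1) − 2.576·√(2·p̄(1−p̄)/n) ] / √( [p1(1−p1) + p2(1−p2)]/n ) }, where p̄ is the mean of p1 and p2.

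- d = 1.0: p1 = 0.309, p2 = 0.691. (0.383 − 0.288)/0.1033 = 0.92, so power is 0.82.
- d = 0.88: p1 = 0.330, p2 = 0.670. (0.340 − 0.288)/0.1051 = 0.495, so power is 0.69.

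Exact check: sum the probabilities of all pairs of Binomial(40) counts (i, j) for which 80(i − j)²/[(i + j)(80 − i − j)] exceeds 2.576² = 6.635.

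| | d = 0.88 | d = 1.0 |
|---|---|---|
| t-test | 0.90 | 0.96 |
| Chi-square, best cut-off | 0.70 | 0.82 |
| Same, Yates correction | 0.61 | 0.76 |
| Chi-square, 10% control responders | 0.56 | 0.72 |
| Chi-square, 5% control responders | 0.36 | 0.53 |

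The cut-offs of 25%, 33% and 50% are fixed in section 4.1, and nothing places them at the optimum.

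**3. What the responder test needs at 40 per arm for 90% power (two-sided 0.01).** For control rates of 10, 20, 30 and 40%, the treated rate must be 47, 61, 72 and 81%. The differences are 37, 41, 42 and 41 percentage points.

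**4. Sensitivity to d.** At d = 1.2 the best-cut chi-square power is 0.947, and at 1.5 it is 0.996. At d = 1.2 the means comparison has Φ(1.2 × 4.472 − 2.576) = Φ(2.79) = 0.997. A larger effect therefore closes the gap, but it also takes the means test well above 0.90.

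**The case against.** The strongest objection is that 12.2 also names a t-test on change from baseline for the same A-versus-B comparison at Day 6, and nothing in 12.1 attaches the 0.90 to the chi-square test. This stands. A reader might infer that the trial's primary comparison has only 70 to 82% power. The protocol does not support that, because a test of the kind that 12.1 sizes is already planned.

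Second, 0.70 and 0.82 are not unconditional ceilings. The protocol words the 10% as relative to control and gives no control mean. On PaO2/FiO2, where entry allows any value below 350, an assumed control mean of 200 to 300 makes 10% equal to 20 to 30 units, or 2 to 3 SD. Best-cut chi-square power is then above 0.999. This stands too, although the printed 0.90 would then describe neither test. Sidedness is also unstated: a one-sided version at 10 units gives 0.88, still just below 0.90.

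Third, a reader might take the 10% as a 10-point difference in responders. The next sentence of 12.1 gives a variance and an SD in units, so the protocol does not state that hypothesis.

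Fourth, the analysis plan may rank the tests, and 12.2 says of the gradient cut-offs only that they will be summarised. That does not remove the point. The protocol itself names chi-square for improvement without qualification and prints one power figure, calculated on inputs that cannot serve that test.

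**Conclusion.** The point holds as a mismatch between the power statement and one of the two named tests. The 0.90 can describe only a comparison of means, and the protocol does not say so. Where a means test has exactly 0.90, chi-square has at most about 0.70, which is 20 points less. Where 10% means 10 units, it has at most 0.82 against 0.96 for the t-test, which is 14 points less. Stricter cut-offs lower it further.

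These sizes rest on a normal outcome, equal SD, two-sided testing, no missing data and the stated readings of the effect. That no responder rate enters 12.1 needs none of these assumptions. The finding does not show that the trial is underpowered on its t-test, nor that 12.1 overstates the power of a means comparison: on the 10-unit reading it understates it.

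**What to change.** In section 12.1, state that the power figure applies to the two-group comparison of mean Day 6 oxygenation. Give the scale of the 10%: the oxygenation measure, its units and the assumed control mean. Say also whether the SD of 10 refers to the Day 6 value or to the change from baseline, since the t-test in 12.2 uses the change.

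In section 12.2, name that t-test as the powered primary comparison. Label the chi-square tests at 25%, 33% and 50% as supportive and not covered by the stated power. Add that, at 40 per arm and two-sided 0.01, they need a responder difference of about 37 to 42 percentage points for 90% power (control rates 10 to 40%). Carry the same wording into the analysis plan.

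The cost is a few sentences, with no extra patients or data. The downside is a less favourable power figure printed beside the responder tests.
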